2.1. Study Rationale

An open label, single-arm trial to determine if simultaneous administration of acoustic vibration and oscillating expiratory pressure (using Sinusonic device) affects the severity of facial pain among patients with complaint of sinus headache was recently conducted. Twenty-nine patients (mean age 49 years, 55% female) completed this preliminary study without any major adverse events. At 4-weeks follow-up, facial pain visual analog scale (VAS) improved from mean standard deviation(SD) of 59.6+-15.7 to 34.6+-21.7(p<0.001) and approximately 70% of patients achieving a minimal clinically important difference (MCID) across all metrics. Eighty-six percent of subjects would use device again and recommend it to others. As the next step, we propose a randomized controlled trial. Preliminary data demonstrates that the device is low-risk, with high patient satisfaction, and patients are able to perform the intervention at home with ease. The next step to determine device efficacy for the indication of sinus headache is to perform a randomized, controlled, clinical trial.

2.2. Background

The SinuSonic device utilizes acoustic vibration with oscillating expiratory pressure and was first studied for the indication of nasal obstruction. A previous study of acoustic vibrations with oscitating expiratory pressure found significant improvements in objective and subjective metrics of nasal congestion/obstruction suggesting that physiologic changes may occur within the nasal cavity in response to device use. There have been two studies from separate institutions investigating use of acoustic vibrations on nasal congestion and interestingly patients noted improvement in secondary symptoms of facial pain and pressure. Although these study were focused on patients with nasal congestion, subjects improvements in facial pressure was an interesting finding. The question thus arose whether a device employing simultaneous acoustic vibrations and positive expiratory pressure to the nasal cavity could improve symptoms in patients with chief complaint of sinus headache. We recently conducted an open label trial to determine if simultaneous administration of acoustic vibration and oscillating expiratory pressure (using Sinusonic device) affects the severity of facial pain among patients with complaint of sinus headache. Twenty-nine patients (mean age 49 years, 55% female) completed our preliminary study without any major adverse events. At the 4-week follow-up, facial pain visual analog scale (VAS) improved from mean standard deviation(SD) of 59.6+-15.7 to 34.6+-21.7(p<0.001) and approximately 70% of patients achieving a minimal clinically important difference (MCID) across all facial pain metrics. Eighty-six percent of subjects would use device again and recommend it to others. As the next step, we propose a randomized controlled trial. Preliminary data demonstrates that the device is low-risk, with high patient satisfaction, and patients are able to perform the intervention at home with ease.

2.3. Benefit/Risk Assessment

Based on available clinical studies, application of acoustic vibration with positive end expiratory pressure to the nasal cavity is a relatively low-risk intervention. In two separate studies investigating its use for nasal congestion, no adverse events were reported in 90 subjects. In a more recent study looking specifically at patients with sinus headache, one patient noted mild epistaxis that resolved following use.

Similarly, four patients noted some mild-moderate discomfort during device use. No permanent or major adverse events were noted.

More detailed information about the known and expected benefits and risks and reasonably expected adverse events (AEs) of SinuSonic device may be found in the package insert and summary of product characteristics.

2.3.1. Risk Assessment

Theoretical risks of device use include transient discomfort, nasal irritation, and epistaxis. In order to minimize risks, patients with any nasal crusting or ulceration on exam, or history of severe epistaxis will be excluded from the study.

2.3.2. Benefit Assessment

Benefits include the potential for this therapy to be efficacious in treating sinus headache and offer a low-risk solution with minimal side effects.

2.3.3. Overall Benefit Risk Conclusion

Taking into account the measures taken to minimize risk to participants participating in this study, the potential risks identified in association with the SinuSonic device are justified by the anticipated benefits that may be afforded to participants with Sinus headache.

3. Objectives, Endpoints, and Estimands

Objectives	Endpoints
Primary	

 To determine superiority of SinuSonic intervention versus control in treatment of facial pain for patients with complaint of sinus headache that lack objective evidence of sinonasal inflammation 	
 Change in facial pain visual analogue scale at 8 weeks Change in Brief Pain Inventory Short Form at 8 weeks
Secondary	

 To determine safety of device use 	
 Number and percent of subjects reporting pain with device use Number and percent of subjects reporting epistaxis Change in Nasal Obstruction Symptom Evaluation (NOSE) Score at 8 weeks
Tertiary	

 To determine device use satisfaction 	
 Number and percent of subjects that would use the device again Number and percent of subjects that would recommend the device to others

Primary estimand

The primary clinical question of interest is:

What is the improvement in facial pain measured by facial pain VAS, and BPI-SF in patients with sinus headache treated with SinuSonic device versus a sham device regardless of discontinuation of investigational intervention for any reason and regardless of initiation of rescue medication or change in background medication.

The estimand is described by the following attributes:

- Population: Patients with complaint of sinus headache lacking objective evidence of sinonasal inflammation of nasal endoscopy or imaging
- Endpoint: change from baseline to 8 weeks in facial pain VAS, and BPI-SF
- Treatment condition:

the investigational interventions regardless of discontinuation for any reason, with or without rescue medication or change in background medication (treatment policy strategy).

- Remaining intercurrent events:

The intercurrent events “intervention discontinuation for any reason” and “initiation of rescue medication or change in background medication (dose and product)” are addressed by the treatment condition of interest attribute. There are no remaining intercurrent events anticipated at this time.

- Population-level summary:

difference in mean changes between treatment conditions

Rationale for estimand: Facial pain is the primary complaint impacting quality-of-life in patients with sinus headache. Thus, we propose using 3 validated pain metrics to assess response to therapy. , .

Secondary estimand(s)

The clinical question of interest is for the secondary objective :

What is the difference in the proportion of sinus headache patients experiencing adverse events of pain and epistaxis between investigational SinuSonic treatment arm compared to sham control arm.

The estimand is described by the following attributes:

- Population:

Patients with Sinus Headache

- Endpoint:

Number and percent of subjects reporting pain with device use. Number and percent of subjects reporting epistaxis.

Nasal obstruction symptom evaluation (NOSE) Score change

- Treatment condition:

the investigational interventions regardless of discontinuation for any reason, with or without rescue medication or change in background medication (treatment policy strategy)

- Remaining intercurrent events:

- The intercurrent events “intervention discontinuation for any reason” and “initiation of rescue medication or change in background medication (dose and product)” are addressed by the treatment condition of interest attribute. There are no remaining intercurrent events anticipated at this time

- Population-level summary:

Difference in proportion of patients experiencing adverse event

Rationale for estimand: Safety is a secondary endpoint and will be assessed by specifically tracking incidence of pain with device use and epistaxis. These adverse events are based on prior study results.

4. Study Design

4.1. Overall Design

- This is a parallel, two-arm, sham placebo controlled multicenter (Mayo AZ, Mayo FL and Mayo RST), clinical trial investigating use of the novel SinuSonic Device for sinus headache.
- The control group will be a sham device of similar appearance to the investigational device
- Participants will be healthy volunteers with complaint of sinus headache lacking objective evidence of sinonasal inflammation on exam or endoscopy
- Primary outcome measures of facial pain measured using facial pain VAS and BPI-SF will be assessed at baseline, Day 1, 2 week, 4 week, 6 week, and 8 weeks.
- Participants will be randomized in a 1:1 fashion; SinuSonic arm: Sham device, respectively.
- Total Duration of study participation will be 11 weeks; 2-3 weeks for screening and randomization and 8 weeks for the intervention component.

4.2. Scientific Rationale for Study Design

Sinus headaches are a widely prevalent condition and accounts for a significant portion of Otolaryngologic clinic visit. Patients lacking objective evidence of sinonasal inflammation are thought to have a primary headache disorder. The direct and indirect socioeconomic costs of headache are estimated at 14 billion dollars per year. Established barriers to headache therapy include failure to consult the appropriate subspecialty professional, failure to arrive at a specific diagnosis, and lack of appropriate acute and preventative therapy.(Dodick) There are frequently long wait times for patients to see neurologists. Many otolaryngologists are unfamiliar with prescribing neuroactive medications. From a patient's perspective, there is stigma associated with a diagnosis of headache disorders making it difficult sometimes for patients to accept this reality. SinuSonic utilizes acoustic vibration with positive end expiratory pressure and has been shown to improve subjective and objective measures of nasal obstruction. Interestingly, multiple studies using similar technology found improvements in patients complaining of facial pain. This led to a single-arm study investigating the devices use for treatment of sinus pain and results demonstrated a significant benefit across three pain metrics. The next logical step is to perform a randomized, sham-controlled trial. The parallel design comparing the investigational device to a sham device is best practice. The primary endpoint of interest includes facial pain measured by facial pain VAS, and BPI-SF, two validated pain metrics. The primary end point of facial pain patient reported questionnaires directly impacts and assesses how patients feel and function. In order to be inclusive, all male and female patients 18 years and older are eligible to participate.

4.3. Justification for Dose

For this device, the term *dose* refers to the number of 3-minute treatment sessions.

Justification for device use is based on manufacturer's recommendation and efficacy with use in prior studies. The device will be turned on and silicone nasal mask placed over the nose and participants will breathe similar to their baseline nasal breathing against the device for 2 doses (two 3-minute treatment session). The device will be used twice daily, any the protocol will not allow any deviations in treatment.

4.4. End-of-Study Definition

The end of the study is defined as the date of the last questionnaire submission of the last participant in the.

A participant is considered to have completed the study if the participant has completed all periods of the study including submitting the final questionnaire, which is after 4 weeks of device use.

5. Study Population

Prospective approval of protocol deviations to recruitment and enrollment criteria, also known as protocol waivers or exemptions, is not permitted.

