	
 Percent achieving a minimal clinically important difference Adverse events reported via questionnaire (pain, epistaxis, etc.) Percentage willing to use again and recommend device to others Nasal obstruction symptom evaluation (NOSE) Score change

Overall Design:

This is a parallel, placebo-controlled multicenter randomized trial. The study population will consist of healthy volunteers with sinus headache/pain lacking objective evidence of chronic sinusitis. This will be a single-blinded study blinded to the participants. Because this study will involve minimal intervention from the investigators (i.e. participants will fill out surveys remotely), there will be minimal influence from the investigators and analysts end. Participants will be randomized to the treatment or the sham-placebo arm and the device they received (either device or sham), will be recorded in a secure database. Following screening, investigational intervention assignment will be performed by randomization in a 1:1, investigational device: sham ratio. Data will be collected and stored in an electronic data storage system.

Brief Summary:

The purpose of this study is to measure facial pain/pressure with a novel device using acoustic vibrations with oscillating expiratory pressure compared with a sham device in participants with sinus pain/headache lacking objective evidence of sinonasal inflammation.

Study details include:

- The study duration will be up to 12 months.
- The treatment duration will be up to 8 weeks.

- The visit frequency will be 0 visits. Participants will fill out questionnaires fielded via an electronic data capture system at 1 week, 2 weeks, 3 weeks, and 4 weeks of device use.

[figure not shown]
Number of Participants:

Approximately 120 participants will be screened to achieve 60 enrolled.

A maximum of 60 participants will be enrolled

Study Arms and Duration:

The total duration of study participation with screening, run-in (i.e., delivery of device), and device use is 11 weeks. Participants will use the investigational or sham device for 2 minutes, twice-daily for the entire 8-week study duration.

Data Monitoring/Other Committee:**1.2. Schema**

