7.3.1. Time Period and Frequency for Collecting AE and SAE Information

All SAEs will be collected from the start of study intervention until exit from the study at the timepoints specified in the SoA (Section 1.3).

All AEs will be collected from the start of study intervention until the exit from study at the timepoints specified in the SoA (Section 1.3).

Medical occurrences that begin before the start of study intervention but after obtaining informed consent will be recorded as medical history/current medical conditions, not as AEs.

All SAEs will be recorded and reported to the sponsor or designee immediately and under no circumstance should this exceed 24 hours, as indicated in Appendix 1. The investigator will submit any updated SAE data to the sponsor within 24 hours of it being available.

Investigators are not obligated to actively seek information on AEs or SAEs after conclusion of the study participation. However, if the investigator learns of any SAE, including a death, at any time after a participant has been discharged from the study, and the investigator considers the event to be reasonably related to the study intervention or study participation, the investigator must promptly notify the sponsor.

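### Section 4.4 and the synopsis place the last questionnaire at 4 weeks, but the primary endpoints need Week 8, so a participant could count as a completer without a primary endpoint value

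*Combined protocol and SAP*

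**What the plan says.** Two places stop the questionnaires at four weeks. Section 4.4 counts a participant as having completed the study on "submitting the final questionnaire, which is after 4 weeks of device use". The Brief Summary in the synopsis describes "questionnaires fielded via an electronic data capture system at 1 week, 2 weeks, 3 weeks, and 4 weeks of device use", and nothing later.

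Everything that defines the primary analysis uses eight weeks:

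- The synopsis objective concerns facial pain after eight weeks of use, and the synopsis has participants using the device "twice-daily for the entire 8-week study duration".
- Section 3 times both primary endpoints at eight weeks and defines the estimand endpoint as "change from baseline to 8 weeks in facial pain VAS, and BPI-SF".
- Section 4.1 says that VAS and BPI-SF "will be assessed at baseline, Day 1, 2 week, 4 week, 6 week, and 8 weeks".
- The SoA (Section 1.3) has an 8-week intervention period, with VAS and BPI-SF marked through Week 8. NOSE is marked at baseline and Week 8 only.
- The primary null hypothesis in Section 8.1 is stated at eight weeks.

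Sections 8.3.1 and 8.3.1.1 exclude missing data points from the analysis.

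**The concern.** VAS and BPI-SF are participant-completed questionnaires, so the questionnaire schedule is the collection schedule for the primary data. A completion rule that names a Week 4 questionnaire as the last one does not protect the Week 8 value. If that value is absent, the change from baseline to Week 8 does not exist for that participant. The analysis drops the participant, and the disposition table still reports a completer. The completion rate would then say nothing about how much primary endpoint data are present. NOSE is exposed in the same way, because it has no other post-baseline assessment. A one-week-recall score that was not collected at Week 8 cannot be recovered later.

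**Working it through.** The plan states no figure on this point, so the check compares passages.

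**1. Questionnaire times side by side**

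| Source | Times after the start of device use |
|---|---|
| Synopsis, Brief Summary | Weeks 1, 2, 3, 4 |
| Section 4.4, final questionnaire | Week 4 |
| Section 4.1 | Day 1, Weeks 2, 4, 6, 8 |
| SoA, VAS and BPI-SF | Day 1, Weeks 2, 4, 6, 8 |
| SoA, NOSE | Week 8 |
| Section 3, primary endpoints and estimand | Week 8 |
| Section 8.1, primary hypothesis | Week 8 |

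The synopsis list and the SoA share Weeks 2 and 4. Weeks 1 and 3 are in the synopsis only. Day 1, Week 6 and Week 8 are in the SoA only. The primary time point is therefore one of those missing from the synopsis list. The synopsis also disagrees with itself: it has eight weeks of device use and an eight-week objective, but no questionnaire after Week 4.

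**2. The completion rule taken literally**

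Section 4.4 sets two conditions: the participant has "completed all periods of the study including submitting the final questionnaire", and that questionnaire falls at four weeks. Consider a participant who uses the device for all eight weeks, submits the Week 4 questionnaire and submits nothing afterwards.

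- All periods completed: met, if a period is completed by using the device through it.
- Final questionnaire, dated to four weeks: met.
- Week 8 VAS and BPI-SF: absent, so Week 8 minus baseline cannot be formed.
- Analysis: excluded as missing under Sections 8.3.1 and 8.3.1.1.

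The participant is a completer without a primary endpoint value.

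**3. Could the phrase mean some time later than four weeks?**

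Grammatically it could. But the synopsis lists "at 1 week, 2 weeks, 3 weeks, and 4 weeks of device use" and stops there, which makes Week 4 the natural reading. The looser reading would still not require a Week 8 questionnaire.

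**4. Which schedule prevails**

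The opening of Section 7 refers to the SoA for procedures and their timing and makes adherence to it mandatory. Section 7.1 refers to it for all efficacy time points. A site or EDC build that follows the SoA collects Week 8. One that follows the synopsis list does not.

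**5. Size**

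The documents describe no EDC build and report no site practice, and Section 8.4 makes no allowance for missing data. Neither a number of lost Week 8 values nor a loss of power can be derived from them.

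**The case against.** The strongest reply is that these are two stray sentences in an otherwise consistent eight-week plan. Section 4.4 also demands completion of every study period, the SoA has an 8-week intervention period, and Sections 7 and 7.1 make the SoA the reference for timing. A team working from the SoA would collect Week 8 and lose nothing.

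Much of that stands, and it makes the loss conditional. It does not remove the defect. The pointers to the SoA govern when assessments are made, whereas Section 4.4 says who counts as a completer, and its own sentence dates the last questionnaire. The four-week timing also appears in two separate sections. The open-label pilot had a four-week follow-up, so carried-over text is a plausible explanation, but that is inference.

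A reader might infer several stronger things that the documents do not support:

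- *Adverse event collection stops at Week 4.* Section 7.3.1 says "All AEs will be collected from the start of study intervention until the exit from study", but the same sentence continues by tying collection to the SoA time points, and the SoA places adverse event review in the 8-week intervention period.
- *The study itself, and hence the analysis, ends at Week 4.* The end-of-study date in Section 4.4 is the last participant's last questionnaire submission, with no four-week figure attached. If Week 8 questionnaires are collected, it falls after them.
- *Half of the device exposure falls after completion.* This ignores the requirement to complete all periods.
- *Remote questionnaires are the only source of data.* The synopsis has zero visits, but Sections 6.5, 6.10, 6.11 and 7.2 describe visits, and Section 6.5 describes direct questioning at them.
- *Satisfaction and adverse event rates are fixed at Week 8 throughout.* Only Section 8.1 times them there. As extracted, the SoA marks satisfaction under early discontinuation.

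**Conclusion.** The contradiction is real and sits in operative text. As written, Section 4.4 permits a completer with no Week 8 VAS or BPI-SF, and the synopsis questionnaire list omits the primary time point. Whether any Week 8 data are lost depends on whether sites or the EDC system follow those two passages instead of the SoA, and the documents do not say.

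A reader might go further and conclude that none of the 60 participants would have a primary endpoint, or might put a fraction on the loss. The first needs a build that ignores the SoA and Section 4.1, and no build is described. The second needs an assumed fraction with no basis in the documents. It also fits poorly with a single shared system, whose schedule would affect everyone or no one. No size should be attached to this point. It warrants correction because the exposed value is the primary endpoint and the correction is small.

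**What to change.** Three changes:

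1. In Section 4.4, replace the reference to four weeks of device use with the Week 8 questionnaire, using the SoA window of +/- 3 days.
2. In the synopsis Brief Summary, replace the weekly questionnaire times with those in the SoA: Day 1 and Weeks 2, 4, 6 and 8.
3. Check the EDC questionnaire schedule against the SoA, in particular that Weeks 6 and 8 are present and that NOSE is issued at Week 8.

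The cost is a wording amendment in two places and one configuration check. No assessment is added, because the SoA already contains all of these time points, and no treatment rule changes.

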5.1. Inclusion Criteria

Participants are eligible to be included in the study only if all of the following criteria apply:

1. Participant must be ≥ 18 years of age inclusive, at the time of signing the informed consent.
2. Participants who are overtly healthy as determined by medical evaluation including medical history and physical examination.
3. Capable of giving signed informed consent
4. Facial pain or pressure for ≥ 3 months of symptom duration
5. Pain/pressure VAS score of ≥ 5
6. Lund MacKay Score of ≤ 3 with no single sinus score of 2

